Oro-facial clefts	Q35*-Q37*
Cleft lip with or without cleft palate	Q36*, Q37*
Cleft palate	Q35*
Digestive system	Q38*-Q45*, Q79.0
Esophageal atresia with or without trachea-	Q39.0, Q39.1
esophageal fistula	
Duodenal atresia or stenosis	Q41.0
Atresia or stenosis of other parts of small intestine	Q41.1, Q41.2, Q41.8
Ano-rectal atresia and stenosis	Q42.0-Q42.3
Hirschsprung's disease	Q43.1
Atresia of bile ducts	Q44.2
Annular pancreas	Q45.1
Diaphragmatic hernia	Q79.0
Abdominal wall defects	Q79.2, Q79.3, Q79.5*
Gastroschisis	Q79.3
Omphalocele	Q79.2
Urinary	Q60*, Q61**, Q62**, Q63*, Q64**, Q79.4
Bilateral renal agenesis including Potter syndrome	Q60.1, Q60.6
Multicystic renal dysplasia	Q61.4
Congenital hydronephrosis	Q62.0
Bladder exstrophy and/or epispadias	Q64.0, Q64.1*
Posterior urethral valve and/or prune belly	Q64.2, Q79.4
Genital	Q50**, Q51***, Q52***, Q54*, Q55**, Q56*
Hypospadias	Q54*
Indeterminate sex	Q56*
Musculoskeletal	Q65**, Q66***, Q67*, Q68*, Q69*, Q70**,
	Q71***, Q72***, Q73*, Q74*, Q75*, Q76***,
	Q77*, Q78*, Q79**
Limb reduction defects	Q71***, Q72***, Q73*
Club foot – talipes equinovarus	Q66.0*
Hip dislocation and/or dysplasia	Q65.0*, Q65.1, Q65.2, Q65.80, Q65.81
Polydactyly	Q69*
Syndactyly	O70**
Other anomalies/syndromes	
Skeletal dysplasias	Q74.0?, Q77*, Q78.0?, Q78.2-Q78.8
Silving aj opinoino	\(\cdot\), \(\cdot\), \(\cdot\), \(\cdot\), \(\cdot\), \(\cdot\)

EUROCAT subgroups	ICD-10 code
Craniosynostosis	Q75.0
Congenital constriction bands/amniotic band	Q79.8?
Situs inversus	Q89.3
Conjoined twins	Q89.4
Congenital skin disorders	Q80*-Q82*
VATER/VACTERL	Q87.2?
Laterality anomalies	Q20.6, Q24.0, Q33.8?, Q89.0?, Q89.3
Teratogenic syndromes with malformations	Q86*, P35.0, P35.1, P37.1
Fetal alcohol syndrome	Q86.0
Valproate syndrome	Q86.8?
Maternal infections resulting in malformations	P35.0, P35.1, P37.1
Genetic syndromes and microdeletions	Q44.7?, Q61.9?, Q74.8?, Q75.1, Q75.4, Q75.8?,
-	Q87**, Q93.51?, D82.1
Chromosomal	Q90*, Q91*, Q92**, Q93**, Q95*-Q99*
Down syndrome	Q90*
Patau syndrome/trisomy 13	Q91.4-Q91.7
Edwards syndrome/trisomy 18	Q91.0-Q91.3
Turner syndrome	Q96*
Klinefelter syndrome	Q98.0-Q98.4

^{*} Indicates how many additional decimal places should be included in the wildcard, including the number listed. For instance, Q93

Codes that were included in the MACDP ICD-9 code list but are no longer classified as congenital malformations in the new ICD-10 categorization will be considered for inclusion, with clinician input if possible.

- E78.71 Barth syndrome
- E78.72 Smith-Lemli-Opitz syndrome
- M21.021 Valgus deformity, not elsewhere classified, right elbow
- M21.022 Valgus deformity, not elsewhere classified, left elbow
- M21.029 Valgus deformity, not elsewhere classified, unspecified elbow
- M21.121 Varus deformity, not elsewhere classified, right elbow
- M21.122 Varus deformity, not elsewhere classified, left elbow
- M21.129 Varus deformity, not elsewhere classified, unspecified elbow
- P02.8 Newborn affected by other abnormalities of membranes
- P29.3 Persistent fetal circulation (typically a birth complication and not a defect)

Postnatal growth deficiency

- E34.30 Short stature due to endocrine disorder, unspecified

^{**} should include the following: Q93 (non-billable), Q93.0, Q93.1, Q93.2, Q93.3, Q93.4, Q93.5 (non-billable), Q93.51, Q93.59, Q93.7, Q93.8 (non-billable), Q93.81, Q93.82, Q93.88, Q93.89, Q93.9.

[?] Inclusion to be considered with clinician consultation.

-	E34.31	Constitutional short stature
-	E34.32	Genetic causes of short stature
-	E34.321	Primary insulin-like growth factor-1 (IGF-1) deficiency
-	E34.322	Insulin-like growth factor-1 (IGF-1) resistance
-	E34.328	Other genetic causes of short stature
-	E34.329	Unspecified genetic causes of short stature
-	E34.39	Other short stature due to endocrine disorder
-	M89.20	Other disorders of bone development and growth, unspecified site
-	M89.21*	Other disorders of bone development and growth, shoulder
-	M89.22*	Other disorders of bone development and growth, humerus
-	M89.23*	Other disorders of bone development and growth, ulna and radius
-	M89.24*	Other disorders of bone development and growth, hand
-	M89.25*	Other disorders of bone development and growth, femur
_	M89.26*	Other disorders of bone development and growth, tibia and fibula
-	M89.27*	Other disorders of bone development and growth, ankle and foot
-	P05.0* below but	Newborn light for gestational age (newborn light-for-dates; weight length above 10th percentile for gestational age)
_	P05.2 for gestation	Newborn affected by fetal (intrauterine) malnutrition not light or small onal age
-	P05.9	Newborn affected by slow intrauterine growth, unspecified
-	P92.6	Failure to thrive in newborn
-	R62.50 childhood	Unspecified lack of expected normal physiological development in
_	R62.51	Failure to thrive (child)
-	R62.52	Short stature (child)

with abnormal findings

• Infant developmental delay

R62.59

Z00.71

- F80.0 Phonological disorder
- F80.1 Expressive language disorder

PFIZER CONFIDENTIAL

Other lack of expected normal physiological development in childhood

Encounter for examination for period of delayed growth in childhood

^{*}indicates wildcard, to include all sub-codes

-	F80.2	Mixed receptive-expressive language disorder
_	F80.4	Speech and language development delay due to hearing loss
_	F80.81	Childhood onset fluency disorder
_	F80.82	Social pragmatic communication disorder
-	F80.89	Other developmental disorders of speech and language
_	F80.9	Developmental disorder of speech and language, unspecified
-	F70	Mild intellectual disabilities
-	F71	Moderate intellectual disabilities
-	F72	Severe intellectual disabilities
-	F73	Profound intellectual disabilities
-	F78.A1	SYNGAP1-related intellectual disability
-	F78.A9	Other genetic related intellectual disability
-	F79	Unspecified intellectual disabilities
-	R41.83	Borderline intellectual functioning
-	F82	Specific developmental disorder of motor function
-	F84.0	Autistic disorder
-	F84.2	Rett's syndrome
-	F84.3	Other childhood disintegrative disorder
-	F84.5	Asperger's syndrome
-	F84.8	Other pervasive developmental disorders
-	F84.9	Pervasive developmental disorder, unspecified
-	F88	Other disorders of psychological development
-	F89	Unspecified disorder of psychological development
-	R41.842	Visuospatial deficit
-	R41.843	Psychomotor deficit
-	R62.0	Delayed milestone in childhood
-	Z13.40	Encounter for screening for unspecified developmental delays
_	Z13.41	Encounter for autism screening
-	Z13.42	Encounter for screening for global developmental delays (milestones)
-	Z13.49	Encounter for screening for other developmental delays

Document Approval Record

Document Name: C4671038_PROTOCOL AMENDMENT 3_20NOV2024

Document Title: C4671038_PROTOCOL AMENDMENT 3_20NOV2024

Signed By:	Date(GMT)	Signing Capacity
[name]	20-Nov-2024 15:27:23	Manager Approval
[name]	22-Nov-2024 13:01:16	EUQPPV Approval

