9.3. Variables

9.3.1. Outcomes

The primary outcome is MCM. The secondary outcomes are SA, induced termination, stillbirth, livebirth, SGA, preterm birth, postnatal growth deficiency and

infant developmental. The study outcomes will be identified by ICD-10 diagnosis and procedure codes, CPT^{®2} procedure codes, and HCPCS procedure codes on claims. All outcomes will initially be identified via claims-based algorithms. Potential cases of MCM, induced termination, SGA, preterm birth, postnatal growth deficiency and infant developmental delay, and a sample of livebirths identified via claims-based algorithms will be adjudicated via medical records.

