9.7.3. Missing data

This study is based on an analysis of automated medical and prescription claims, supplemented by information abstracted from medical records. Using the standard approach in claims data analyses, the presence of a medication or disease claim will be assumed to indicate use of that medication or the presence of that disease and conversely, the absence of a medication or disease claim will indicate the absence of use of that medication or a diagnosis of that disease. Outcome data may be missing due to health plan disenrollment, or non-linked infants and missing or limited medical records. Sensitivity analyses are planned to assess the degree of bias potentially introduced by non-linkage of infants and missing or non-informative medical records. All retrieved medical records will be reviewed for mention of MCMs, as pregnancies that result in non-livebirths may not always capture MCMs in medical claims.

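### Annex 2 lists R62.50 (and very probably R62.59) only under postnatal growth deficiency, so an infant whose delay carries no other listed code has no stated route into the developmental delay count

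*Protocol*

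**What the plan says.** Section 9.3.1.2 of the Protocol defines SGA and preterm birth in words. It only names postnatal growth deficiency and infant developmental delay, so the Annex 2 code lists are their sole operational definitions.

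- **Growth list.** It contains R62.50, "Unspecified lack of expected normal physiological development in" childhood. Beside it stand R62.51, "Failure to thrive (child"), and R62.52, short stature. The text around R62.59, "Other lack of expected normal physiological development in childhood", is scrambled, but code order and the neighbouring delayed-growth encounter code place it in this list.
- **Delay list.** From the R62 family it holds R62.0, "Delayed milestone in childhood". It also takes several non-specific codes, among them F88 and F89, "Unspecified disorder of psychological development", as well as F82 and the developmental screening encounters Z13.40, Z13.41, Z13.42 and Z13.49. R62.50 is absent.

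On ascertainment, Section 9.3.1 states: "All outcomes will initially be identified via claims-based algorithms". It then sends to record review "Potential cases of MCM, induced termination, SGA, preterm birth, postnatal growth deficiency and infant developmental delay", along with a sample of livebirths. Section 9.7.1 says that the claims definitions for outcomes to be validated by record review are meant to be highly sensitive so that every potential event is captured. It expects interim counts to be too high as a result. Section 9.7.2.3 bases the primary comparisons on outcomes that are chart-confirmed or come from validated algorithms, and also presents claims-identified analyses.

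**The concern.** The R62.50 label describes a general lack of expected development. The two growth meanings in the same block have codes of their own, R62.51 and R62.52, so nothing in the residual code's label limits it to growth. The delay list already accepts other unspecified codes, which makes the absence of this one look like an omission.

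Chart review can remove a false positive. It cannot add an infant who was never flagged for the outcome. The question is therefore whether some infants with delay are screened for growth only and never counted as delay. Estimating the risk of each infant outcome is part of secondary objective 1 (Section 8), and Section 5 records that both outcomes were added at the regulator's request. A gap in the screen bears directly on that estimate.

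**Working it through.** The plan states no figure for either outcome, since Tables 1 and 2 have no row for them. There is nothing to reproduce, and the check is mainly a reading of the lists against the ascertainment rules.

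**Step 1: the route of one infant.** Take an infant with delay whose only relevant claim is R62.50.

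- Annex 2: flagged as potential growth deficiency, not as potential delay.
- Section 9.3.1: the record is reviewed for the outcome for which the infant is a potential case.
- Section 9.3.1.3: the review form holds the elements needed to confirm the outcome diagnosis, and the site asked for the record is the one most likely to confirm case status.
- Section 9.7.3: the one stated reading of charts across outcomes is "All retrieved medical records will be reviewed for mention of MCMs".

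No sentence moves this infant into the delay count. The overcount disclosed in Section 9.7.1 is an error in the other direction and does not cover a missed case.

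**Step 2: when the route closes.** The infant is missed only if no other listed delay code appears during infant follow-up. R62.0, F82, F88 or F89 would flag the infant as delay, and so would a Z13.4x screening encounter on its own.

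**Step 3: size of the loss, by assumption.** Let s be the share of delay cases carrying only R62.50 or R62.59. The documents give no value, so the range is illustrative. If s is the same in both cohorts:

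- counted risk = true risk × (1 − s);
- ratio = [2p(1 − s)] / [p(1 − s)] = 2.0, unchanged for a true ratio of 2.0;
- increase in the standard error of the log ratio ≈ 1/√(1 − s) − 1 (rare-outcome approximation, both case counts scaled by 1 − s).

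| s | counted / true risk | ratio | SE increase |
|---|---|---|---|
| 0.05 | 0.95 | 2.0 | 2.6% |
| 0.20 | 0.80 | 2.0 | 11.8% |
| 0.40 | 0.60 | 2.0 | 29.1% |

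**Step 4: the growth side, by assumption.** Let p be the true growth deficiency prevalence in the comparator. Let f be the share of infants without growth deficiency who are flagged only through these codes, equal in both cohorts. With a true ratio of 2.0:

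- observed comparator prevalence = p + (1 − p)f;
- observed exposed prevalence = 2p + (1 − 2p)f.

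Middle case, p = 0.05 and f = 0.01: 0.05 + 0.95 × 0.01 = 0.0595 and 0.10 + 0.90 × 0.01 = 0.109. Comparator prevalence is inflated 0.0595/0.05 = 1.19 times, and the ratio appears as 0.109/0.0595 = 1.83.

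Over p from 0.02 to 0.10 and f from 0.0025 to 0.03, the extremes are:

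- p = 0.10, f = 0.0025: 0.10225 and 0.202; inflation 1.02 times, ratio 1.98;
- p = 0.02, f = 0.03: 0.0494 and 0.0688; inflation 2.47 times, ratio 1.39.

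All p and f values are assumptions. If f is zero, because the codes are in practice used for growth problems, there is no inflation at all.

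**The case against.** The strongest reply is that the placement is defensible and the consequence small. The label speaks of physiological development, which can mean growth, and R62.51 and R62.52 in the same block are growth codes. The delay list is broad, and its screening-encounter codes can flag an infant before any diagnosis. This stands, and it limits the point to infants with none of those codes.

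A reader might infer that delay coded with R62.50 or R62.59 is never screened. The documents do not support that, because any other listed delay code brings the infant in.

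A reader might also infer that claims-based growth deficiency is inflated by infants who grow normally. That depends on how the codes are used, on which the documents are silent. Interim overcounting is disclosed, and the primary comparison requires confirmed cases or a validated algorithm. That safeguard is partial: Section 9.3.1.3 expects records for about 35% to 42.5% of the database and seeks at most 550, and claims-identified results are presented as well.

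Section 9.7.3 could be read as barring a chart reader from noting delay. It does not. It adds a reading for MCMs and is silent on other outcomes. The gap is the lack of a stated route, not a prohibition.

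Finally, Section 9.3.1.3 allows the algorithms to be revisited. That leaves room for the correction but does not make it.

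**Conclusion.** The point holds as a modest gap in the screening list. R62.50 is listed under one outcome although its label could fit either. R62.59 very probably shares its position, but that is inferred from code order in a broken table; R62.50 alone sustains the point. An infant with delay and no other listed delay code has no stated route into the delay count, contrary to the plan's own sensitivity aim.

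The size is unknown and may be small. The shares used in the illustration have no source in the documents. A non-differential loss lowers the delay risk and widens its interval but leaves the ratio alone. A growth overcount, and the dilution that would come with it, is conditional on coding practice. It would be unsupported to conclude that both outcomes are shown to be mis-measured, or that the codes belong to delay rather than growth. Only these two secondary outcomes are touched; MCM and the sample sizes in Section 9.5 are not.

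**What to change.** In Annex 2, list R62.50 and R62.59 as screening codes under both postnatal growth deficiency and infant developmental delay. On the record review form, have the adjudicators assign each infant flagged by these codes to delay, growth deficiency, both or neither. Show claims-only results for each outcome with and without the two codes. If the sponsor prefers the present placement, state the reason for leaving the codes out of the delay list. Moving them wholly to delay in claims-only analyses is not advised, because it would replace one untested assignment with another.

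The cost is a two-code change, one item on the form and one extra set of claims-only results. No new infants are flagged, since these are already potential growth cases. There are two downsides. Claims-only delay counts that include the codes become less specific. And Section 9.3.1.3 requests one record from one provider per case, so a record chosen for growth may not document development.
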